## **ASSESSMENTS.**

**VR Task Measures:** The VR game has built-in performance measures, including but not limited to the total time spent on completing the specified task (e.g., find out avatar's birthday at the bus stop), number of errors following the sequential steps, number of successful social interactions with avatars and deviation from specified scenarios. The number of difficulty levels mastered by the participant will determine the overall performance. We will track the VR scores per session to determine the rate of learning.

### **Social Assessments:**

(1) **Social Functioning Scale (SFS)** has 79-items with 7 subscales: social engagement, interpersonal communication, daily living activities, recreation, social activities, independent living and employment. Raw scores of the subscales are

converted to scaled score ( $m=100$ ,  $SD=15$ ). **(2) Social Emotional Task from CogState** (SET-CS) is a facial emotion recognition task within CogState (see below). **(3) Bell Lysaker Emotion Recognition test (BLERT)**. Subjects view 10s vignettes of an actor talking about life. After each vignette, subjects select one emotion that was portrayed. There are 3 different stories portrayed in 7 emotions (21 total). Correct responses are summed. **(4) Revised Eyes Test (EYES)** assesses the theory of mind. It asks subjects to decide the mental state of a person from an image of his/her eyes. For each set of eyes, subjects select one word out of 4 choices that best describes what the person in the picture is thinking or feeling. There are 36 trials. These measures were selected for their validity, reliability, and coverage of important domains of social functioning. Our VR game simulates and exercises social interactions, thus, targeting emotion recognition (BLERT, EYES, SET-CS), and theory-of-mind (EYES, BLERT). Practicing these skills will likely lead to broad, beneficial consequences for social functioning (SFS).

**Cognitive Assessments:** **(1) Wechsler Abbreviated Scale of Intelligence (WASI)** will estimate IQ at t1. It will not be repeated at t2 or t3. Baseline IQ may interact with the efficacy of social interventions. **(2) CogState** is a computerized, standardized battery for assessing cognitive abilities ([cogstate.com](http://cogstate.com)). It reliably detects cognitive changes over time, and shows minimal practice effects with repeated administrations. It is widely used to measure cognition in treatment trials. Results are automatically scored. It takes 30 minutes.

**Clinical Symptoms:** SAPS and SANS will be used to measure the severity of symptoms in SZ.

**Satisfaction Survey:** To obtain feedback about VR experience, we will give a 9-item survey that asks about difficulties, hurdles, enjoyment and motivational factors, and solicits suggestions.

## **DATA ANALYSIS PLAN**

Does the VR intervention elicit significant pre-post change on the targeted social attention, measures of social functioning (SFS, SET-CS, BLERT, EYES) and clinical symptoms (SAPS and SANS)? What are the specific treatment parameters that provide the optimal benefit when cost-benefit and other considerations are taken into account? To address training effects on the social assessments, we will use a linear mixed effects model (LMM) analytic approach because it allows for maximally flexible modeling of effects and parameters and for a principled treatment of missing data. To address this question, we will conduct repeated measures LMM analyses. Specific contrasts will directly assess: **1)** The linearity of the slope of change within each group; **2)** Pairwise differences among time points within each group; and, **3)** Group differences in linearity and pairwise differences. Because our power calculations indicate that the most powerful tests of group differences will be provided by an ANCOVA framework (with pre-treatment values serving as the covariate), we will also use this analytic approach to compare the two dose conditions. Although it is important to minimize Type 2 errors in an initial study, we will also generate multiplicity-corrected p values across the 5 primary measures using simulation-based approaches. A similar approach will be used to analyze the clinical symptom and other measures (e.g., CogState) although a generalized linear mixed effects (GLMM) model may be needed to accommodate non-normal distributional properties of the measures. With a particular emphasis on the set of social measures,

we will also conduct analyses that assess effects on the set as a whole. Depending on the correlational structure of the measures, we will either: **1)** Form 1 or 2 linear composites using prior findings on the dimensional structure of the measures and our own analyses; or **2)** Conduct a multivariate analysis of variances using the flexible facilities of mixed-effects software to accommodate such models. We will assess clinically meaningful change by comparing the post-treatment SZ and normative distribution for each group. To provide a more fine-grained assessment of the proximal effects of training we will assess change over days on the VR task measures (e.g., # of difficulty levels mastered) to assess the rate of learning across, within, and between the dose conditions. Generalized linear and generalized nonlinear mixed effects models will be used to carefully assess the functional form of change over time using several approaches: **a)** Polynomial growth models; **b)** Penalized spline analyses; and, **c)** Non-linear mixed effects models directly estimating parameters particularly relevant to learning. It is important that analyses also address missing data and attrition because: (1) Minimization of drop-out is one of the goals of the VR intervention and will be an important determinant of the dose and duration to use in the R33 phase; and (2) To minimize biases, it is important to use a principled approach to the treatment of missing data on the other outcome measures. We will: (1) Conduct logistic regression and, if feasible, discrete survival analyses predicting drop-out based on weekly data; (2) Use pattern-mixture models and related approaches to estimate treatment effects in the presence of drop-out and assess how different patterns of attrition might moderate effects; and, (3) Try to include in models auxiliary variables that predict drop-out. Supplementary analyses will also test whether performance changes during the training phase mediate the effects of the intervention conditions on social functioning and symptom measures.

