## **PROTOCOL**

We will implement the adaptive social VR game and determine the optimal dose. After we construct each subject's affective model with the machine-learning algorithm, we will test the effects of the adaptive VR games in 40 medicated outpatients with schizophrenia (SZ). Demographically matched control (CO) subjects (n=16) will only participate in the affective modeling and social and cognitive assessments but not in VR training (see Human Subjects section for details). To determine the optimal dose of VR training, it is necessary to conduct a valid assessment for social functioning pre- and post- treatment. Details of assessments are outlined below. Optimal dose of physiology-based, adaptive VR intervention is unknown but Tsang & Man reported that just ten 30-minute sessions of conventional, non-adaptive VR training was sufficient to obtain an improvement in SZ. In our study, we will examine the effects of social VR training on social and cognitive measures, pre- and post-treatment. At baseline (t1), the PI's will use stratified randomization to assign SZ to two dose conditions: high vs. low. Stratified randomization is used to ensure that potential confounding factors (e.g. age, gender) are evenly distributed between groups. If possible, we will try to match the two groups on IQ, and the Social Functioning Scale, a broad measure of social functioning, but if it cannot be done, we will statistically adjust for them when we test for treatment effects. Everybody will train twice a week but the low dose group will train for 30 mins and the high dose group for 2 x 30 mins per visit. VR task performance will be recorded at each visit. At t1, social, cognitive and symptom assessments will be conducted. The research staff who administer assessments are blind to the group assignment and SZ are unaware which group they are in. The research assistants who supervise VR sessions will NOT conduct assessments because they will be aware of the dosing. After t1, subjects play the VR game for 2.5 weeks, at which point (t2), we repeat the social, cognitive and symptoms assessments plus a satisfaction survey. Then they train for another 2.5 weeks. At 5 weeks (t3), we repeat the assessments and the satisfaction survey. The behavioral measures have been used in intervention trials to be reliable across time with minimal practice effects, or offer alternate forms. The satisfaction survey will solicit user feedback to improve our protocol in the future.

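### Two unranked dose comparisons are planned, and the ANCOVA, presented as the more powerful, has no stated outcome visit, analysis set or missing-data handling

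*Combined protocol and SAP*

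**What the plan says.** In the Protocol section, "the PI's will use stratified randomization to assign SZ to two dose conditions: high vs. low". The 40 patients are assessed at baseline (t1), at 2.5 weeks (t2) and finally: "At 5 weeks (t3), we repeat the assessments and the satisfaction survey". A patient lost during the second half can therefore still have a t2 score.

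The Data Analysis Plan selects a repeated-measures LMM for the social measures because "it allows for maximally flexible modeling of effects and parameters and for a principled treatment of missing data". Its third set of contrasts already compares the doses: "Group differences in linearity and pairwise differences". The description mentions no baseline covariate.

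The same paragraph then cites power calculations, not shown, as favouring an "ANCOVA framework (with pre-treatment values serving as the covariate" for tests of group differences, and says this approach will also be used to compare the doses. It does not name the post-treatment visit analysed, the patients included or the handling of missing scores. It does not rank the ANCOVA against the LMM.

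Later in the section the plan states that, to limit bias, "it is important to use a principled approach to the treatment of missing data on the other outcome measures". It commits to models predicting drop-out, pattern-mixture models for treatment effects, and auxiliary variables. None of these is tied to the ANCOVA.

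**The concern.** Finding the better dose is the purpose of this phase, and two tests of it are planned with no rule for disagreement. Calling one of them the most powerful invites readers to rely on it, and that is the one with no missing-data provision.

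A conventional ANCOVA of t3 on baseline uses only patients who have t3. Suppose patients who have improved little by t2 leave more often from one arm. The remaining patients in that arm are then a favourable selection, and the ANCOVA flatters that dose. A likelihood-based model that includes t2 as an outcome corrects for this, provided drop-out depends only on what has been observed. The plan treats drop-out as one of the things that will determine the dose and duration for the next phase, so drop-out related to dose is a live possibility.

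**Working it through.** **No figure to reproduce.** The documents give no effect size, SD, correlation, alpha or drop-out rate. From the documents: 40 patients, two arms, visits t1, t2 and t3. Assumed: 20 per arm, SD 1, two-sided 5%, and the correlations and drop-out rates below.

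**Step 1: the gain from baseline adjustment.** With complete data, a between-arm contrast of change from t1 to t3 has variance 2(1−ρ)·2/n. ANCOVA has (1−ρ²)·2/n. The ratio is 2/(1+ρ): 1.33 at ρ = 0.5, 1.18 at 0.7, 1.11 at 0.8. The stated preference for ANCOVA therefore makes sense against an LMM that leaves the baseline means free by arm. The plan does not say whether its LMM does.

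**Step 2: precision under random loss.** Let n2 and n3 be the patients per arm with t2 and with t3, and pc the t2–t3 correlation given baseline.

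- ANCOVA on t3: v = (1−ρ²)·2/n3.
- Baseline-adjusted repeated measures: v = (1−ρ²)·2·[(1−pc²)/n3 + pc²/n2].
- Ratio of the second to the first: 1 − pc²(1 − n3/n2).

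With all correlations 0.7, pc = 0.7/1.7 = 0.412 and pc² = 0.170. At 20% drop-out (n3 = 16), the ratio is 1 − 0.170 × 0.2 = 0.966 if every drop-out has t2, and 1 − 0.170 × (1 − 16/18) = 0.981 if half do. Power for a 0.8 SD difference, Φ(0.8/√v − 1.96), is 94.3% with no loss, 88.7% with completer ANCOVA, and 89.2% to 89.7% with repeated measures. For ρ from 0.5 to 0.8 and drop-out from 10% to 30%, the variance saving is 0.6% to 6%.

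If t2–t3 correlate 0.8 and the other pairs 0.6, pc = (0.8 − 0.36)/(1 − 0.36) = 0.688 and pc² = 0.473. With n2 = 19 and n3 = 16, the ratio is 1 − 0.473 × 3/19 = 0.925, so ANCOVA variance is 8% higher. The same losses with all correlations 0.7 give 3%. Simulation under equal random loss gave about 3% to 9%.

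**Step 3: bias.** Simulation: 4,000 trials per row, true difference 0.20 SD at t2 and 0.40 SD at t3, 5% random loss before t2. Later loss is logistic in t2 change, with slope 1 log-odds per SD. The repeated-measures estimate regresses t2 on arm and baseline, then t3 on arm, baseline and t2, and combines them as b3(arm) + b3(t2)·b2(arm).

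| Correlations | Drop-out after t2, low vs high dose* | ANCOVA bias (SD) | Repeated measures |
|---|---|---|---|
| all 0.7 | 10% vs 30% | +0.04 | under 0.01 |
| t2–t3 0.8, others 0.6 | 10% vs 30% | +0.07 | under 0.01 |
| all 0.7 | 5% vs 35% | +0.06 | under 0.01 |
| t2–t3 0.8, others 0.6 | 5% vs 35% | +0.11 | under 0.01 |
| either | same mechanism in both arms | about 0.02 or less in size | under 0.01 |

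*Rates at average t2 change. Total loss by t3 is heavier: about 18% to 19% vs 34% to 36%, and 12% to 13% vs 38% to 40%, depending on how the average is centred.

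The slope matters: bias is nil at slope 0 and exceeds 0.11 SD at steeper slopes.

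**Step 4: a different mechanism.** True difference 0.50 SD (0.25 at t2). Low-dose loss is 10% at random, and high-dose loss is 1/(1 + exp(0.9 + 1.5·t2 score)), about 19% overall. ANCOVA bias was +0.071, +0.071 and +0.057 SD at ρ = 0.5, 0.7 and 0.8. Repeated measures gave −0.008, +0.001 and +0.004.

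**Step 5: scale.** The standard error in Step 3 was about 0.27 to 0.30 SD. So the bias is 0.04/0.27 = 0.15 to 0.11/0.30 = 0.37 of a standard error, or 0.04/0.40 = 10% to 0.11/0.40 = 28% of the assumed effect.

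**The case against.** The text supports less than a reader might infer, in five respects.

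- **That the dose comparison has been moved to ANCOVA.** It has not. The ANCOVA is additional, and the LMM keeps a dose contrast.
- **That the plan discards everyone without the final visit.** No completer rule is stated. An ANCOVA framework could be fitted as a mixed model with baseline as covariate, which is the proposed fix. This stands: the gap is in specification. But the plan sets the ANCOVA apart from the LMM, so the conventional reading is natural, and if the other was meant, saying so costs nothing.
- **That the plan contradicts its own missing-data principle.** Too strong, given the planned pattern-mixture models and auxiliary variables. What remains is that these are not linked to the ANCOVA, and with about 20 per arm pattern-mixture models serve better as sensitivity analyses than as the repair of a main test.
- **That the plan expects drop-out to differ by dose.** It does not say so. It treats drop-out as something to study. The bias needs drop-out that is both t2-dependent and unequal by arm.
- **That the repeated-measures model avoids the loss.** Patients lost before t2 still contribute no outcome data, and the precision recovered is small.

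The bias is also well under half a standard error, and every input behind it is assumed.

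**Conclusion.** The point holds as a specification gap with a better method available. Two dose comparisons are planned without a ranking. The one favoured for power lacks a visit, an analysis set and a missing-data rule, and the one chosen for missing data lacks a stated baseline covariate.

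The size is modest and conditional on a t3 completer ANCOVA. The main reason to change is protection from bias, and precision is secondary. The model's protection rests on drop-out depending only on observed scores. The gap should be closed before analysis, but it does not invalidate the design.

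**What to change.** State one main dose comparison for each measure: the arm difference at t3 (and at t2) from a single repeated-measures LMM with

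- t2 and t3 scores as outcomes;
- visit as a category, arm, and arm-by-visit;
- baseline score and baseline-by-visit;
- an unstructured covariance for the two visits;
- a small-sample degrees-of-freedom correction, such as Kenward-Roger, given about 40 patients;
- all randomised patients with any post-baseline score.

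Keep a t3 ANCOVA, if wanted, only as a sensitivity analysis beside the planned pattern-mixture models, and say that it uses patients with t3. The LMM contrasts on within-group slopes and pairwise changes can stay as descriptive results.

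The cost is SAP wording, with the same mixed-model software. With complete data the t3 estimate equals the ANCOVA estimate, so the power advantage the plan seeks is kept.

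### Do the VR error and success counts need a common time base before the 30-minute and 60-minute dose groups are compared?

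*Combined protocol and SAP*

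**What the plan says.** All references are to the combined protocol and SAP.

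- **Exposure (PROTOCOL).** Visits are equally frequent in both arms: "Everybody will train twice a week". Their length is what separates the doses: "the low dose group will train for 30 mins and the high dose group for 2 x 30 mins per visit". Training lasts 5 weeks.
- **Recording (PROTOCOL).** "VR task performance will be recorded at each visit".
- **Measures (ASSESSMENTS, VR Task Measures).** The list has the time taken on a specified task and then "number of errors following the sequential steps, number of successful social interactions with avatars and deviation from specified scenarios". The same paragraph makes the count of levels mastered the determinant of overall performance, and adds: "We will track the VR scores per session to determine the rate of learning".
- **Analysis (DATA ANALYSIS PLAN).** "we will assess change over days on the VR task measures (e.g., # of difficulty levels mastered) to assess the rate of learning", with the comparison covering the "rate of learning across, within, and between the dose conditions". Generalized linear and nonlinear mixed models are planned, with no link function or exposure term named.
- **Mediation (DATA ANALYSIS PLAN).** Supplementary analyses will "test whether performance changes during the training phase mediate the effects of the intervention conditions on social functioning and symptom measures". The mediating measure is not named.

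**The concern.** Two of the listed measures are raw counts with no denominator, and the two arms are observed for different lengths of time at every visit. If a count is the total for the visit, a high-dose patient has twice as long to make errors and to complete interactions. At equal skill the counts would then differ 2-fold from the first visit, before any training could have acted.

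That difference would be exposure, not learning. On successes the high dose would look better and faster. On errors it would look worse in level yet quicker to improve, so the two measures would point in opposite directions. A mediator built from such counts would carry a dose-to-performance path created by the clock, and an indirect effect could be declared when dose changes neither skill nor outcome. In a study meant to choose a dose, that deserves a check.

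**Working it through.** The plan gives no power figure, effect size or count rate for the VR measures, so there is no stated figure to reproduce.

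**1. Exposure.** 2 visits a week x 5 weeks = 10 visits. Low dose: 10 x 30 = 300 minutes. High dose: 10 x 60 = 600 minutes. Ratio 600/300 = 2.0, the same at each visit.

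**2. Which unit does the plan use?**

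| Reading of the count | Minutes, low / high | Ratio at equal skill |
|---|---|---|
| Total over the visit | 30 / 60 | 2.0, if events accrue in proportion to time |
| Per 30-minute session | 30 / 30 | 1.0 |
| Per task or scenario | not tied to minutes | no built-in difference |

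The PROTOCOL sentence says when performance is recorded, not that two blocks are summed. The ASSESSMENTS sentence ties the learning rate to the session. The only session length in the documents is 30 minutes (for a cited earlier study), and the high dose is written as two 30-minute units. So the 2-fold difference belongs to one of three readings, and no text selects it.

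**3. What happens to the learning rate under the worst reading?** Let m(t) be the mean count per 30 minutes at visit t, equal in both arms, and let k = 1 (low) or 2 (high). The visit total has mean k x m(t).

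- Raw scale: slope of k x m(t) = k x slope of m(t). The ratio is 2 if there is learning; with no learning both slopes are 0.
- Log scale: log(k x m(t)) = log k + log m(t). The dose intercept moves by log 2; the slope does not move.

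**4. Simulation with exponential growth.** Assumed: 20 per arm (the plan gives 40 patients and no ratio), 10 visits, Poisson counts, 5 or 10 events per 30 minutes at the first visit, log-growth 0, 0.05 or 0.10 per visit, between-patient SD 0.3 on the log scale, no dose effect on skill, 400 replicates.

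| Quantity | Visit totals | Per 30 minutes |
|---|---|---|
| High/low level ratio | 2.01 to 2.02 | 0.99 to 1.02 |
| Raw slopes, high vs low (base 10, growth 0.05) | 1.328 vs 0.659 | 0.657 vs 0.659 |
| Log slopes, same case | 0.05 vs 0.05 | 0.05 vs 0.05 |
| Raw slopes falsely different, with learning | 76 to 100% | 4 to 7% |
| Raw slopes falsely different, no learning | 4 to 7% | 6% |

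**5. Simulation with linear growth.** Assumed: bases of 5, 10 and 20 per 30 minutes, a 50% rise or fall over training, slope CV 50, 75 or 100%. On visit totals, per-patient raw least-squares slopes differed falsely between doses in about 30 to 92% of trials. Per-patient Poisson log-slopes on the same totals, with no offset, did so in 3 to 6%, against a nominal 5%.

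**6. Would an offset help?** With scheduled minutes the offset is log 30 or log 60, constant within an arm. In a log-link model it moves only the dose intercept, by log 60 - log 30 = log 2, and leaves every slope unchanged.

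**7. Mediation.** With visit totals, a raw count slope as mediator and an assumed skill-outcome correlation of 0.3, 0.5 or 0.7, a false indirect effect was declared in 13-17%, 30-40% or 39-63% of simulated trials; with rates, in 1-5%. None of those conditions is in the plan. The plan says what determines overall VR performance, and it is levels mastered. That is a cumulative achievement, where more levels from more practice may be a real effect of dose.

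**The case for a change.** The best case for a change is this. The analysis sentence gives levels mastered only as an example, so the counts are in scope. No link is fixed, so a raw-scale model is permitted. No rule combines the two blocks of a high-dose visit. Two analysts could follow the plan and reach opposite conclusions, and a sentence of text would prevent that at no cost in data.

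Much of this stands. The unit is undefined, the three sections use visit, session and day without reconciling them, and the mediator is unnamed. With visit totals, a comparison of count *levels* between doses would be off by a factor of 2 even under a log link, and would need a rate or an offset.

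It does not follow that the plan prescribes a wrong analysis. The harm needs visit totals, accrual in proportion to time, and a raw-scale slope or a comparison of levels, all together. The second is doubtful: errors are framed around task steps and scenarios, and the game is adaptive with rising difficulty. The third departs from the usual link for counts and from the stated target, which is rate of learning. A rate has limits too. If the second half-hour runs 10, 20 or 30% slower, the per-30-minute ratio at equal skill is (1 + 0.9)/2 = 0.95, 0.90 or 0.85, and a rate does not adjust for the difficulty reached.

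**Conclusion.** No change to the plan is needed. The 2-fold figure is right as arithmetic for visit totals under proportional accrual, but no stated rule produces it. On the session reading the ratio is 1.0. On the visit reading, log-scale slopes are still comparable between doses, with false differences in 3 to 6% of simulated trials. The 30 to 100% and 13 to 63% figures describe raw-scale analyses of visit totals under assumed count levels, learning, variability and correlations; they are not expected results of this plan.

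The gap is missing detail in secondary and supplementary analyses. An analyst who knows that one arm plays for twice as long will choose a per-session or per-minute unit before comparing count levels, and will take levels mastered as the natural mediator. The mixed-model and ANCOVA comparisons of the social measures do not depend on it. This rests on the counts being modelled on a log scale or in a common time unit; an analysis of raw visit totals would need to be read with the 2-fold exposure in mind.

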
**VR Training:** SZ will play the "Day Out" game in the lab. Biosensors and eye tracking will be used. To boost adherence, we will call/text 2 hours before the visit. They will be paid after each visit and receive a bonus upon reaching the next level of difficulty in the game, and when they complete the training.

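### The drop-out models name no sparse-event method: if drop-out is about 10% or less, a default logistic fit will often give no usable dose effect, although drop-out is to inform the R33 dose

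*Combined protocol and SAP*

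**What the plan says.** The Protocol section states that "we will test the effects of the adaptive VR games in 40 medicated outpatients with schizophrenia (SZ"), and that stratified randomisation will "assign SZ to two dose conditions: high vs. low". It gives no allocation ratio. Follow-up runs to the third assessment: "At 5 weeks (t3), we repeat the assessments and the satisfaction survey".

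The Data Analysis Plan gives drop-out two roles. It is a target in itself: "Minimization of drop-out is one of the goals of the VR intervention", and the result "will be an important determinant of the dose and duration to use in the R33 phase". It also matters for handling missing data on the other outcomes. The analysis named for it is to "Conduct logistic regression and, if feasible, discrete survival analyses predicting drop-out based on weekly data". The condition of feasibility attaches to the survival version only.

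The plan gives no expected drop-out rate, no list or limit of predictors for this model, no estimator, and no fallback for the logistic model if events are few. The pattern-mixture models and auxiliary variables in the same section deal with bias in the other outcomes when data are missing. They do not deal with sparse events in the drop-out model.

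**The concern.** The plan works to keep drop-out low. Besides the stated goal, the VR Training section describes reminders ("To boost adherence, we will call/text 2 hours before the visit"), payment after each visit and bonuses. If these succeed, a trial of 40 patients will produce only a few drop-outs, and one dose arm may have none. Logistic regression fitted in the usual way then has no finite estimate for the dose effect, and its Wald test means nothing. With a few more events the model can be fitted, but several predictors on a handful of events push the odds ratios away from 1.

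At stake is one of the few results that the plan ties to a later design decision. In the favourable case of low drop-out, the named analysis may return nothing usable on how the two doses compare, and a substitute would have to be chosen after the failed fit has been seen.

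**Working it through.** The documents give no drop-out rate, event count or power figure for drop-out, so there is nothing to reproduce.

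**Inputs**
- 40 randomised patients in two dose arms (Protocol).
- 1:1 allocation, 20 per arm: assumed.
- Common drop-out rate q from 5% to 30%: assumed, shown as a range.
- Default maximum-likelihood fit: assumed, because no estimator is named.

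**1. No drop-outs in at least one arm.** One arm has none with probability (1−q)^20, so at least one arm has none with probability 1 − [1 − (1−q)^20]². At a rate of 10%, one arm has none with probability 0.9^20 = 12.16%. Both arms have at least one drop-out with probability 87.84% squared, which is 77.16%, and the remainder is 22.84%. The number of events in the whole trial is binomial(40, q).

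| Drop-out rate | Expected events | P(an arm has none) | P(fewer than 10 events) |
|---|---|---|---|
| 5% | 2 | 58.8% | >99% |
| 10% | 4 | 22.8% | >99% |
| 15% | 6 | 7.6% | 93% |
| 20% | 8 | 2.3% | 73% |
| 25% | 10 | 0.6% | 44% |
| 30% | 12 | 0.2% | 20% |

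The third column includes trials with no drop-out in either arm, where there is nothing to model: (1−q)^40, which is 12.9% at a rate of 5% and 1.5% at 10%. Exactly one empty arm, which gives an infinite odds ratio, therefore has probability 46% at 5% (58.8% less 12.9%) and 21% at 10% (22.8% less 1.5%).

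**2. More predictors.** Simulated 40-patient trials were checked for separation with dose, age and gender in the model (balanced gender, normal covariates, no true effects). It occurred in about 70–72% of trials at 5% drop-out, 32–34% at 10%, 13–14% at 15%, 4% at 20% and 1–2% at 25%. Adding IQ and the Social Functioning Scale changed little. These predictor sets are assumptions, taken from the factors named for stratification or matching. True predictors of drop-out would raise the figures.

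**3. Bias when the fit succeeds.** A simulation used five predictors (arm, one binary, three continuous), a true log odds ratio of 0.70 for arm and modest covariate effects. At 20% drop-out about 7% of fits failed, and the mean estimate among the rest was 0.85. At 25% the figures were about 2% and 0.90. The inputs are again assumed.

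**4. Weekly survival model.** With a separate effect for each of five weeks and a constant hazard, at least one week has no drop-out, so that its effect cannot be estimated, in 95% of trials at 10% drop-out and 68% at 20%. A smooth or constant baseline hazard avoids this.

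**5. What the data can still say.** Take 0/20 against 3/20. Ordinary logistic regression gives an infinite odds ratio. The risk difference is 15 points with a Newcombe 95% interval from minus 4 to plus 36 points, and the exact two-sided p is 0.23. With arm as the only predictor, a Firth fit amounts to adding 0.5 to each cell. The odds become 3.5 to 17.5 (0.200) in one arm and 0.5 to 20.5 (0.0244) in the other, so the odds ratio is finite, at about 8.2.

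**6. Precision.** For 2/20 against 5/20 the model fits, yet the risk difference of 15 points has an interval from minus 9 to plus 38 points. With true rates of 10% and 30%, Fisher's exact test has about 24% power at 20 per arm, and 80% power needs about 62 per arm (normal approximation).

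**The case against.** A reader might infer that the planned models will often fail, whatever happens in the trial. The documents do not support that. They give no drop-out rate, and with dose alone in the model an empty arm is uncommon at 15–20% and rare from 25% upwards. A reader might also infer that the plan specifies maximum likelihood. It says only logistic regression, and a penalised fit is also logistic regression. The default is inferred because no alternative is named. Nor can the survival analysis be faulted for being infeasible, since the plan fits it only if feasible. All three limits stand, and the conclusion is worded to respect them.

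It is also fair to say that an inestimable odds ratio hides nothing. The counts remain visible, drop-out is one consideration among several in choosing the dose, and the regression serves the missing-data work too. This lowers the stakes. It does not supply the missing item: nowhere does the plan commit to the arm difference in drop-out with its uncertainty.

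The 2/20 against 5/20 example shows imprecision at this sample size, not failure of logistic regression, and no choice of method narrows that interval.

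Penalisation has a cost, because it pulls predicted risks toward one half. With 0/20 and 2/20, adding 0.5 per cell gives predicted risks of 0.5/21 = 2.4% and 2.5/21 = 11.9%, an average of 7.1% against 5% observed. The fix has to allow for this.

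**Conclusion.** The point holds in conditional form. If drop-out is about 10% or less, which is the direction in which the plan is working, a default logistic fit gives no finite dose effect in roughly a quarter of trials at a rate of 10% and more than half at 5%, and more often with extra predictors. Between about 15% and 20%, outright failure is uncommon, but fewer than 10 events is the usual case and a model with several predictors will tend to exaggerate. From 25% upwards, failure to fit is a minor issue and imprecision is the main one.

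These figures rest on 20 patients per arm, equal drop-out in the two arms and an unpenalised fit. Unequal rates alter them: an arm is empty in 38% of trials at 5% against 15%, and in 12% at 10% against 30%. This is a worthwhile, low-cost improvement to one analysis. It does not undermine the trial's main comparisons.

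**What to change.** Add to the Data Analysis Plan:

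- Drop-out will be reported as counts by dose arm and as the arm difference in proportion, with a Newcombe or exact 95% confidence interval. This is the drop-out quantity that informs the choice for the R33 phase.
- The logistic model, and the discrete-time model if used, will be fitted by Firth penalised likelihood with profile-likelihood intervals, with arm and at most one or two pre-named baseline predictors. A discrete-time model will use a smooth or constant baseline hazard instead of free week effects.
- Absolute drop-out risks will be taken from the observed proportions or from an intercept-corrected penalised fit, because the penalty shifts predicted risks toward one half.

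The cost is a few sentences and standard software, with no extra patients or data. When events are plentiful, the penalised fit approaches the ordinary one. The change removes the fitting failure, reduces bias and settles the method before the data are seen. It adds no precision, so the text should also say that a wide interval is expected and should be read as such.
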